#### **3.6.4. Definition of Study Day**

The first dose date of VBR and of AB-729 will be calculated where applicable. Study Day 1 is defined as the first dose date of study drug, which is the minimum of the first dose dates of VBR and of AB-729 in a treatment group. If the first dose date is missing, the date of randomization will be used.

The last dose date of VBR and of AB-729 will be calculated where applicable. The last dose date of each drug will be the end date on the respective study drug end of treatment eCRF. The last dose date of study drug will be defined as the maximum of the last dose dates of VBR and of AB-729 in a treatment group.

For the On-Treatment Phase, study day will be calculated from Study Day 1 and derived as follows:

- For days prior to the first dose: Assessment Date – Study Day 1
- For postdose study days: Assessment Date – Study Day 1 + 1

For the Off-Treatment Phase, the Off-Treatment Day 1 will be defined as the day after the last dose date of study drug VBR or 56 days after last dose of AB-729, whichever is later. The off-treatment study day will be calculated from the last dose date and derived as Assessment Date – Off-Treatment Day 1 + 1.

For the NrtI-Restart Phase, the NrtI-Restart Day 1 will be defined as the first dose date of restarted NrtI. The NrtI-Restart study day will be calculated from the first dose of NrtI and derived as Assessment Date – First Dose Date of NrtI + 1.

#### **3.6.5. Analysis Visit Windows**

Subject visits might not occur on protocol-specified days. Therefore, for the purpose of analysis, observations will be assigned to analysis windows. For the On-Treatment Phase, data will be summarized up to Week 48 visit or premature termination visit. For the Off-Treatment Phase, the data will be summarized by treatment action up to the end of study, or up to NrtI restart for applicable patients. For the NrtI-Restart Phase, data will be summarized only for applicable subjects who restarted NrtI after having discontinued AB-729, VBR, or both.

The analysis windows for the On-Treatment Phase assessments of HBV TNA, HBV RNA, HBsAg, Vital signs, Chemistry, Hematology, Coagulation, and Urinalysis are provided in [Table 3-1](#).

For the On-Treatment Phase assessments of HBeAg, only the analysis visits of Baseline and Week 48 will be presented in the summary tables. Any non-baseline on-treatment visit will be categorized under analysis visit Week 48.

**Table 3-1 On-Treatment Phase Analysis Visit Windows for Efficacy (HBV TNA, HBV RNA, HBsAg), Vital Signs, and Laboratory Assessments**

Nominal Visit	On-Treatment Phase Nominal Study Day	Visit Window Study Day	
		Lower Limit	Upper Limit
Baseline	1	(none)	1
Week 2	14	2	21
Week 4	28	22	42
Week 8	56	43	70
Week 12	84	71	98
Week 16	112	99	126
Week 20	140	127	154
Week 24	168	155	182
Week 28	196	183	210
Week 32	224	211	238
Week 36	252	239	266
Week 40	280	267	294
Week 44	308	295	322
Week 48	336	323	350
Week 52	364	351	378
Week 56	392	379	≥392

The analysis windows for the On-Treatment Phase assessments of HBV DNA, HBcrAg, and electrocardiogram (ECG) are provided in [Table 3-2](#).

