#### **3.6.2. Definition of Baseline**

In general, Baseline will be defined as the last non-missing evaluation prior to the first dose on Day 1. Change from Baseline will be defined as the result at desired timepoint minus the result at Baseline.

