#### **3.6.3. Definition of Study Phase and End of Study**

The analyses will include all the data collected in this study based on three phases defined as follows.

- **On-Treatment Phase:** when a subject is undergoing treatment with AB-729, VBR, or both per treatment group (ie, from first dose of either study drug through the last dose of VBR +1 day or last dose of AB-729 +56 days, whichever is later)
- **Off-Treatment Phase:** after a subject has discontinued AB-729, VBR, or both per treatment group, and prior to NrtI restart if applicable (ie, after the last dose of VBR +1 day or last dose of AB-729 +56 days, whichever is later, until the end of study or before the first dose of NrtI if it was restarted)
- **NrtI-Restart Phase:** after a subject has restarted NrtI, following the Off-Treatment Phase (ie, from the first dose of restarted NrtI through the end of study)

End of study is defined as when the last subject completes the last follow-up or is considered “lost to follow-up”, whichever is later.

Subjects may prematurely discontinue study drug earlier prior to the Week 48 visit. The end dates of the On-Treatment Phase may vary for individual subjects based on their last dose dates as defined in [Section 3.6.3](#).

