#### **6.1.2. Analysis Methods for Efficacy Endpoints**

The observed and mean change in  $\log_{10}$  HBV RNA, HBV TNA, HBsAg, HBcrAg, and ALT from Baseline will be summarized using descriptive statistics (sample size, mean, SD, median, Q1, Q3, minimum, and maximum) by phase, treatment group, and treatment action at each visit.

For the On-Treatment Phase, analysis will be performed to compare the mean changes of  $\log_{10}$  HBV RNA,  $\log_{10}$  HBV TNA,  $\log_{10}$  HBsAg,  $\log_{10}$  HBcrAg, and ALT from Baseline to each timepoint between VBR+AB-729+NrtI and VBR+NrtI, and between VBR+AB-729+NrtI and AB-729+NrtI. The primary comparison for mean change endpoints will be made using an analysis of covariance (ANCOVA) model, including baseline value, the stratification factors, and treatment group as covariates. The estimated least square means of treatment effects and estimated difference in treatment effects between treatment groups at Week 48 will be presented along with the 95% CIs and p-values. The analysis will be based on observed data.

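### Later off-treatment means cover only subjects who have not restarted NrtI, and no change from end of treatment is reported, so the marker tables may understate rebound

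*Combined protocol and SAP*

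**What the plan says.** - **Stopping and restart (Protocol 4.1.1 and 4.1.2; SAP 1.2).** Subjects who meet the Week 48 criteria stop everything, including NrtI. They restart NrtI for confirmed ALT above 10 × ULN; for raised ALT with raised direct bilirubin or INR; for sustained ALT elevation with HBV DNA above 2000 IU/mL; for decompensation; or at investigator discretion. Follow-up continues to Week 96 after restart.
- **Phases.** SAP 3.6.3 runs the Off-Treatment Phase "until the end of study or before the first dose of NrtI if it was restarted". SAP 3.6.5 adds that "the data will be summarized by treatment action up to the end of study, or up to NrtI restart for applicable patients". Values after restart are kept, but separately: "For the NrtI-Restart Phase, data will be summarized only for applicable subjects who restarted NrtI". That phase has its own clock, because in SAP 3.6.4 "the NrtI-Restart Day 1 will be defined as the first dose date of restarted NrtI".
- **Summaries.** SAP 6.1.2 gives observed values and change for HBV RNA, TNA, HBsAg, HBcrAg and ALT, with sample size, "by phase, treatment group, and treatment action at each visit". Missing data are generally not imputed (SAP 3.5.1).
- **Reference for change.** Baseline is the last evaluation before the first dose, and "Change from Baseline will be defined as the result at desired timepoint minus the result at Baseline" (SAP 3.6.2). No end-of-treatment reference is defined.
- **Day 1 of the phase.** In SAP 3.6.4 "the Off-Treatment Day 1 will be defined as the day after the last dose date of study drug VBR", or 56 days after the last AB-729 dose if that is later.
- **Objective.** Off-treatment durability of response remains a secondary objective in SAP 1.1.

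**The concern.** Durability asks what happens to a marker after treatment stops, in everyone who stopped. The planned off-treatment tables answer a narrower question at each later visit: what is the level among subjects who have not yet needed, or been given, NrtI again? Because restart depends on how the subject is doing, the two answers can differ, and the later means would tend to look better than the experience of all stoppers.

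The only change score runs from before the first dose. It mixes the on-treatment fall with any later rise, so a marker that is climbing after treatment stops can still be shown as a decline. At stake is how far a reader can judge the durability objective from the marker tables. No hypothesis test depends on them.

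**Working it through.** The documents give no restart rate, rebound size or variance for this phase, so there is no planned figure to reproduce. Steps 1, 2 and 5 rest on the text; steps 3 and 4 are illustrations under stated assumptions.

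**1. Who is in a later row.** SAP 3.6.3 and 3.6.5 end a subject's off-treatment data at restart, and nothing is imputed. A later row for the stopping-criteria group therefore contains stoppers minus restarters. Restarters appear in another table counted from their own restart date, so the two tables cannot be lined up by time since stopping. The protocol endpoint that would count restarters, the proportion still off treatment at end of study (Protocol 3.2.2), is not in the SAP 6.1.1 list.

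**2. Whether leaving is related to the marker.** ALT is both a restart trigger and a summarized endpoint, so the link is direct. HBV DNA is a trigger but is not in SAP 6.1.1. HBsAg, HBV RNA, TNA and HBcrAg are not triggers; for them the link depends on how closely they move with ALT and HBV DNA, which the documents do not give.

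**3. Size of the selection effect (log10 markers only, not ALT).** Let f be the fraction restarted, r the mean rebound in restarters and s that in the rest. All stoppers have mean (1 − f)s + fr and the table shows s, so the understatement is f(r − s). With s = 0.2 and r = 1.0 (assumed), f = 0.1, 0.3 and 0.5 give 0.08, 0.24 and 0.40.

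Those values fix the link between restart and rebound by choice. To vary it, assume rebound is normal with mean 0.5 and SD 0.5, and that the fraction f with the highest restart liability leaves, where liability has correlation ρ with rebound. The displayed mean is 0.5 − ρ × 0.5 × φ(z)/(1 − f), with z the normal (1 − f) quantile. For f = 0.5, φ(0)/0.5 = 0.798, so ρ = 0.5 gives 0.5 − 0.5 × 0.5 × 0.798 = 0.30. A simulation of 200,000 subjects gives these displayed mean rebounds:

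| ρ | 10% restarted | 30% | 50% |
|---|---|---|---|
| 0 | 0.50 | 0.50 | 0.50 |
| 0.5 | 0.45 | 0.38 | 0.30 |
| 0.8 | 0.42 | 0.30 | 0.18 |

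Against the true 0.50, the understatement is 0 at ρ = 0, 0.05 to 0.20 at ρ = 0.5, and 0.08 to 0.32 at ρ = 0.8. The comparator is the rebound that all stoppers would have shown without retreatment.

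**4. Effect of the reference.** A subject who falls 2.0 log10 on treatment and regains 1.0 is reported as −2.0 + 1.0 = −1.0. For a group with an on-treatment change of −1.5 (assumed) and a rebound of 0.5, all stoppers average −1.00; the ρ > 0 cells above display −1.05 to −1.32. Each reads as a decline from Baseline while the marker is rising.

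**5. The phase boundary.** Let E be the later of last VBR dose + 1 day and last AB-729 dose + 56 days. SAP 3.6.3 runs the On-Treatment Phase through E and starts the Off-Treatment Phase after E. SAP 3.6.4 labels E itself Off-Treatment Day 1 and numbers a date d as d − E + 1. The first day of the phase, E + 1, is therefore off-treatment day 2, while the Day 1 row in Tables 3-3 to 3-8 ends at day 1. If records are split by phase before windowing, that row is empty. If they are windowed first, the row has no lower limit, and the closest-record rule in SAP 3.6.6 places the last on-treatment value there. The text does not say which order applies. The boundary also matters in Group 3: on nominal days the last AB-729 dose is at day 280, and 280 + 56 = 336 is the Week 48 visit, so a sample drawn slightly late falls outside the On-Treatment Phase.

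**The case against.** A reader might infer that the plan hides rebound. It does not. SAP 6.1.2 shows observed values and sample size at every visit, so levels and a shrinking n are visible. Values up to restart, including those that trigger it, belong to the Off-Treatment Phase (subject to the one-record-per-window rule). Restarters have their own phase summary. SAP 7.2.1.2 tabulates the maximum laboratory grade by phase, which captures ALT flares before restart, and lists graded results by subject. In the single-subject example, a Week 48 row of −2.0 beside a later −1.0 shows the regain. All this stands. What it leaves open is that the Week 48 mean covers all stoppers and a later mean covers some of them, so their difference is not a within-subject change.

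Further points stand in part or in full:

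- Change from Baseline is how Protocol 3.2.2 defines the HBsAg, HBV RNA and HBcrAg endpoints. A second reference is an addition, not the correction of an error.
- A reader might take a fixed bias in log10 units from the arithmetic. The documents do not support one: four of the five markers are not restart triggers, and zero is within the range.
- The study was terminated early, and SAP 1.2 states that the stopping criteria were not applied to subjects reaching Week 48 after the announcement. Few subjects may have late off-treatment visits.
- A reader might conclude that one table keeping post-restart values should replace the current one. That is a choice of estimand. Such values are on NrtI, which may lower the markers again, so a pooled mean could itself understate rebound. The off-treatment clock also runs from VBR and AB-729, not from the NrtI stop date, which the SAP does not derive.
- The Day 1 row is not necessarily empty; step 5 shows a reading under which it is filled.

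**Conclusion.** The point holds as a limit on interpretation. In the stopping-criteria group, later off-treatment means describe subjects who have not restarted NrtI, and restart is driven by outcome. They may understate rebound, clearly for ALT and possibly for the other four markers. Loss of response after stopping is not measured directly by any planned change score, and the SAP contradicts itself on whether Off-Treatment Day 1 lies in the On-Treatment Phase.

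The size is unknown. The illustration of 0.05 to 0.32 log10 rests on an assumed mean and SD of rebound of 0.5, 10% to 50% restarted and a correlation of 0.5 to 0.8; at zero correlation it disappears. Subjects who continued NrtI because they failed the criteria are unaffected. The ANCOVA is confined to the On-Treatment Phase, so no test or sample size is involved. Importance is minor to moderate: the change is cheap and worth making because durability is still a stated objective.

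**What to change.** 1. In SAP 6.1.2, report within-subject change from the last on-treatment value next to change from Baseline.
2. At each off-treatment visit show the number who stopped, the number still off NrtI and the cumulative number restarted, with all stoppers as denominator. Item 1 repairs the reference but not the selection; these counts make the selection visible.
3. Reconcile SAP 3.6.3 and 3.6.4 so that Off-Treatment Day 1 belongs to one phase, and use the last on-treatment value as the reference row. State how a Group 3 Week 48 sample taken after the boundary is handled.
4. Optionally, as supportive only, add one by-visit table on the existing off-treatment clock that keeps post-restart values, flagged as on NrtI.

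The cost is a few table columns and one derived variable, with no new data, since follow-up continues after restart by design. SAP section 1 allows changes made after finalization to be documented in the Synoptic CSR. The downside is that numbers will be small after early termination, so the added columns may be sparse.

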**Table 3-2 On-Treatment Analysis Visit Windows for HBV DNA, HBcrAg, and ECG**

Nominal Visit	On-Treatment Phase Nominal Study Day	Visit Window Study Day	
		Lower Limit	Upper Limit
Baseline	1	(none)	1
Week 12	84	2	126
Week 24	168	127	210
Week 36	252	211	294
Week 48	336	295	≥336

The analysis windows for the Off-Treatment Phase assessments for subjects meeting Treatment Stopping Criteria of HBV DNA, HBV TNA, HBV RNA, HBsAg, Vital signs, Chemistry, Hematology, Coagulation, and Urinalysis are provided in [Table 3-3](#).

**Table 3-3 Off-Treatment Phase Analysis Visit Windows for HBV DNA, HBV TNA, HBV RNA, HBsAg, Vital Signs, Chemistry, Hematology, Coagulation, and Urinalysis for Subjects Meeting Treatment Stopping Criteria**

Nominal Visit	Off-Treatment Phase Nominal Study Day	Visit Window Study Day	
		Lower Limit	Upper Limit
Off-Treatment Day 1	1	(none)	1
Off-Treatment Week 4	28	2	42
Off-Treatment Week 8	56	43	70
Off-Treatment Week 12	84	71	98
Off-Treatment Week 16	112	99	126
Off-Treatment Week 20	140	127	154
Off-Treatment Week 24	168	155	182
Off-Treatment Week 28	196	183	210
Off-Treatment Week 32	224	211	238
Off-Treatment Week 36	252	239	266

Nominal Visit	Off-Treatment Phase Nominal Study Day	Visit Window Study Day	
		Lower Limit	Upper Limit
Off-Treatment Week 40	280	267	294
Off-Treatment Week 44	308	295	322
Off-Treatment Week 48	336	323	≥ 336

The analysis windows for the Off-Treatment Phase assessments of HBcrAg and HBeAg for subjects meeting Treatment Stopping Criteria are provided in [Table 3-4](#).

Table 3-4 **Off-Treatment Phase Analysis Visit Windows for HBcrAg and HBeAg for Subjects Meeting Treatment Stopping Criteria**

Nominal Visit	Off-Treatment Phase Nominal Study Day	Visit Window Study Day	
		Lower Limit	Upper Limit
Off-Treatment Day 1	1	(none)	1
Off-Treatment Week 12	84	2	126
Off-Treatment Week 24	168	127	210
Off-Treatment Week 36	252	211	294
Off-Treatment Week 48	336	295	≥ 336

The analysis windows for Off-Treatment Phase assessments for subjects meeting Treatment Stopping Criteria of ECG are provided in [Table 3-5](#).

Off-Treatment Phase Analysis Visit Windows for HBcrAg and HBeAg for Subjects Meeting Treatment Stopping Criteria

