### 8.3.3 Week 2 Through Week 48 Visits ( $\pm 3$ Days)

The following assessments will be performed at Study Weeks 2, 4, 8, 12, 16, and every 4 weeks thereafter through Week 48 (inclusive) unless otherwise indicated:

- Measure body weight (Weeks 24 and 48 only)
- Record vital signs (temperature, heart rate, respiration rate and blood pressure)
- Complete physical examination (excluding breast and genitalia, unless indicated; Weeks 24 and 48 only); all other visits, symptom-directed physical examination
- 12-lead ECG (Weeks 12, 24, 36, and 48 only)
- FibroScan (if available; Weeks 24 and 48 only)
- Review AEs and concomitant medications

- Obtain blood samples for the following:
  - Safety laboratory tests:
    - chemistry, hematology, coagulation
    - CrCl (Weeks 24 and 48 only)
  - Virology:
    - HBV TNA, HBV RNA, HBsAg, HBsAb (only if HBsAg <LLOQ), HBsAg isoforms and immune complexes, HBV resistance monitoring sample
    - HBV DNA (at Weeks 12, 24, 36, and 48 only)
    - HBeAg, HBeAb, HBsAb, HBcrAg (at Week 48 only)
    - Virology back-up sample (to be used for retesting HBV parameters)
  - Other:
    - FibroTest, APRI (both at Weeks 24 and 48 only)
    - Sparse PK samples for VBR and NrtI
    - Sparse PK samples for AB-729 at 2 hours ( $\pm 1$  hour) postdose (at Weeks 8, 16, 24, and 32 only) and also at Week 40 from subjects who are not participating in the optional intensive PK substudy
    - Blood samples for AB-729 intensive PK substudy (optional) will be collected after the last dose (at Week 40 only) at the timepoints listed in [Section 8.8.5](#)
    - Cytokines/Immune biomarkers (at Weeks 2, 4, 8, 12, 20, 28, 36, and 44 only)
    - PBMCs (at selected sites at Weeks 2, 4, 8, 12, 20, 28, 36, and 44 only; not to be collected at subsequent timepoints if not collected at Day 1)
    - RNAi biomarker
    - Pharmacogenomics sample (optional, at Week 16 only); collected only in subjects who provide additional informed consent and can be collected at a later visit if not collected at Week 16
- Obtain urine samples for the following:
  - Pregnancy test for female subjects of child-bearing potential
  - Urinalysis

- Review subject injection site reaction diary (Groups 1 and 3) at Weeks 2, 12, 20, 28, 36, and 44
- Subject dosing diary
- Assess VBR accountability (Groups 1 and 2)
- Dispense VBR bottles (excluding Week 2); final dispensation at Week 44
- Assessment of Treatment Stopping Criteria (see [Section 4.1.1](#) for details)

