## 8.5 Premature Termination Visit

Should a subject prematurely discontinue their assigned treatment regimen ([Section 7.1](#)) or discontinue from the study ([Section 7.2](#)), a Premature Termination visit should be scheduled. While the Investigator may include additional assessments and evaluations determined by the status of the individual subject, at the minimum, the following assessments should be performed as soon as feasibly possible:

- Record vital signs (temperature, heart rate, respiration rate, and blood pressure)
- Complete physical examination (excluding breast and genitalia, unless indicated)
- 12-lead ECG
- Review AEs and concomitant medications
- FibroScan (if available)
- Obtain blood samples for the following:
  - Safety laboratory tests: chemistry, hematology, coagulation, CrCl
  - Virology: HBV TNA, HBV DNA, HBV RNA, HBeAg, HBeAb, HBsAg, HBsAb (only if HBsAg <LLOQ), HBcrAg, HBsAg isoforms and immune complexes, HBV resistance monitoring sample
  - Virology back-up sample (to be used for retesting HBV parameters)
  - Other:
    - FibroTest, APRI

- Sparse PK sample for VBR and NrtI
  - Cytokines/Immune biomarkers
  - PBMCs (at selected sites only)
  - RNAi biomarker
- Obtain urine samples for the following:
    - Pregnancy test for female subjects of child-bearing potential
    - Urinalysis
  - Subject injection site reaction diary for subjects in Groups 1 and 3
  - Subject dosing diary
  - Assess VBR accountability

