### **6.1. Efficacy Endpoints**

#### **6.1.1. Definition of Efficacy Endpoints**

The efficacy endpoints of Cohort 1 are:

- Mean change in  $\log_{10}$  HBsAg from Baseline at each timepoint
- Mean change in  $\log_{10}$  HBV RNA from Baseline at each timepoint
- Mean change in  $\log_{10}$  HBcrAg from Baseline at each timepoint
- Mean change in TNA quantitative from Baseline at each timepoint
- ALT results and change from Baseline

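### SAP Table 3-2 gives on-treatment HBcrAg Week 12, 24 and 36 windows in which the protocol schedules no sample; any values there would come essentially from early discontinuers

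*Combined protocol and SAP*

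**What the plan says.** **Sampling.** Protocol Section 8.3.3 lists, for the on-treatment visits after Day 1, "HBeAg, HBeAb, HBsAb, HBcrAg (at Week 48 only"). The other two measurements that share the SAP window table are drawn more often: "HBV DNA (at Weeks 12, 24, 36, and 48 only") and "12-lead ECG (Weeks 12, 24, 36, and 48 only"). Protocol Table 9 agrees: HBcrAg is marked at Screening, Day 1, Week 48 and Premature Termination. Protocol Section 8.5 includes both HBeAg and HBcrAg in the Premature Termination virology panel: "HBsAb (only if HBsAg <LLOQ), HBcrAg, HBsAg isoforms and immune complexes". The listed virology panel for unscheduled visits (Section 8.4) contains neither.

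**Windows.** SAP Table 3-2, "On-Treatment Analysis Visit Windows for HBV DNA, HBcrAg, and ECG", applies one set of four post-baseline windows to all three measurements. For HBeAg on treatment, SAP Section 3.6.5 shows only Baseline and Week 48, but adds: "Any non-baseline on-treatment visit will be categorized under analysis visit Week 48". It also keeps data up to the Week 48 or Premature Termination visit in the on-treatment summaries.

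**Use.** Change in log10 "HBcrAg from Baseline at each timepoint" is one of the five efficacy endpoints in SAP Section 6.1.1. Section 6.1.2 summarises it by visit and describes an ANCOVA of changes "from Baseline to each timepoint between VBR+AB-729+NrtI and VBR+NrtI" (and against AB-729+NrtI), on observed data. The least-squares means, differences, confidence intervals and p-values are to be presented at Week 48.

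**The concern.** HBcrAg and HBeAg have the same on-treatment sampling schedule, and the off-treatment window tables (SAP Tables 3-4 and 3-7) treat them together. On treatment the SAP separates them, and neither rule fits the schedule. HBcrAg receives three visits at which nothing is drawn. HBeAg receives the right visits, but the Week 48 window has no lower day limit.

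Followed as written, a programmer would produce HBcrAg rows headed Week 12, Week 24 and Week 36 for each arm. Their content would come essentially from people leaving treatment, under labels that suggest a scheduled assessment of the arm. For HBeAg, a sample taken shortly after the first dose from someone who then stopped would be reported as a Week 48 result. At stake is whether those descriptive rows mean what their labels say.

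**Working it through.** **Step 1: reproduce the windows.** Table 3-2 has nominal Days 84, 168, 252 and 336. Midpoints between neighbours:

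- (84 + 168)/2 = 126
- (168 + 252)/2 = 210
- (252 + 336)/2 = 294

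These match the table's upper limits, so the windows are standard midpoint windows for a 12-weekly schedule. That is the HBV DNA and ECG schedule.

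**Step 2: map scheduled samples into them** (nominal day ±3, Protocol Section 8.3.3 and Table 9).

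| Row | Days | HBV DNA | ECG | HBcrAg |
|---|---|---|---|---|
| Week 12 | 2-126 | Week 12 | Week 12 | none |
| Week 24 | 127-210 | Week 24 | Week 24 | none |
| Week 36 | 211-294 | Week 36 | Week 36 | none |
| Week 48 | 295 onward | Week 48 | Week 48 | Week 48 |

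**Step 3: what else can enter.** The Premature Termination visit is the only protocol-listed source of on-treatment HBcrAg before Week 48. Its sample must fall within the On-Treatment Phase, which SAP Section 3.6.3 ends at the last VBR dose +1 day or the last AB-729 dose +56 days, whichever is later. In Group 2, a visit more than 1 day after the last VBR dose is therefore off-treatment and does not enter Table 3-2.

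**Step 4: distance from the label.** The earliest possible HBcrAg sample in the Week 12 row is 84 − 2 = 82 days early. The earliest possible HBeAg sample in the Week 48 row is 336 − 2 = 334 days early. A lower limit of Day 295 would cap the latter at 336 − 295 = 41 days.

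**Step 5: how many subjects, by assumption.** The documents state no discontinuation rate for this trial. Let r be the proportion stopping by Day 336, with stops spread evenly over Days 2-336 (335 days) and every Premature Termination sample on-treatment. Days 2-294 span 293 days, so the expected number before Day 295 is 60 × r × 293/335.

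| r | Expected of 60 | Week 12 / 24 / 36 rows, all arms | Chance of at least one |
|---|---|---|---|
| 2% | 1.05 | 0.45 / 0.30 / 0.30 | 65% |
| 4.3% | 2.26 | 0.96 / 0.65 / 0.65 | 90% |
| 10% | 5.25 | 2.24 / 1.50 / 1.50 | 99.6% |
| 15% | 7.87 | 3.36 / 2.26 / 2.26 | over 99% |

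The 4.3% is an extrapolation: 2 of 92 subjects stopped over 24 weeks in the VBR extension study (Protocol Section 2.2.3.1), doubled. The largest expected single cell is Group 1, Week 12, at r = 15%: 30 × 0.15 × 125/335 = 1.7 subjects. Each cell would hold roughly 0 to 2 subjects.

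**Step 6: HBeAg.** SAP Section 3.6.6 selects the record closest to the nominal day. A subject with a true Week 48 sample therefore keeps it, and an early sample is used only where there is no later on-treatment one. Besides Premature Termination visits, the unscheduled visits for a confirmed ALT elevation (Protocol Section 9.10.4) can supply HBeAg.

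**The case against.** The best defence is that the mismatch may have no visible effect. With no on-treatment HBcrAg sample before Day 295, the three rows are empty. With one or two, the summaries must show the sample size, so a row of n = 1 or 2 beside a nearly complete Week 48 row gives itself away. This stands, and it limits the point to housekeeping.

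A reader might go further than the documents allow in four ways.

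- **That the HBcrAg treatment comparison is distorted.** Section 6.1.2 does refer to each timepoint, but the presented estimates, intervals and p-values are for Week 48. The ANCOVA uses observed data, so values in the earlier rows do not enter the Week 48 estimates.
- **That the February 2023 termination fills these rows.** SAP Section 1 says active subjects had completed 48 weeks of treatment. SAP Section 1.2 puts the Premature Termination visit at the next follow-up visit for subjects reaching Week 48 after the announcement. Only individual early discontinuation matters here.
- **That the rows can hold nothing but discontinuers.** The unscheduled-visit panel is a minimum, and back-up virology samples are kept for retesting, so an occasional other value is possible. *Essentially* is as far as one can go.
- **That the HBeAg rule harms an efficacy result.** HBeAg is not an efficacy endpoint in the SAP, subjects are HBeAg negative at entry, and the closest-to-nominal rule protects true Week 48 samples.

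Nor does the endpoint's reference to each timepoint need rewording. It is the protocol's own phrase and can be read as each timepoint measured. Recasting follow-up in study weeks would conflict with the SAP, which counts from Off-Treatment Day 1.

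**Conclusion.** The mismatch is certain; its effect is small and conditional. Table 3-2 applies a 12-weekly schedule to a marker drawn on treatment, after Day 1, only at Week 48 and at Premature Termination. Zero scheduled HBcrAg samples can fall in the Week 12, 24 or 36 rows. Whatever appears there would come essentially from subjects who stopped before Day 295 with a Premature Termination sample inside the On-Treatment Phase. Under the assumed 2% to 15% discontinuation with even timing, that is about 1 to 8 subjects over nine cells; under no early discontinuation it is none. The Week 48 HBcrAg estimates stand. The HBeAg labelling fault is secondary and confined to subjects without a true Week 48 sample. This is a correction worth making because it is nearly free, not because a conclusion depends on it.

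**What to change.** Remove HBcrAg from Table 3-2, leaving HBV DNA and ECG. Replace the on-treatment HBeAg rule in SAP Section 3.6.5 with one rule for both markers, for example:

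> For HBcrAg and HBeAg in the On-Treatment Phase, the analysis visits are Baseline and Week 48 (Study Day 295 onward). Post-baseline on-treatment values before Day 295, from premature termination or unscheduled visits, are not assigned to an analysis visit; they are shown in a by-subject listing or a separate premature-termination row.

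Day 295 is suggested because it keeps the Week 48 HBcrAg row as Table 3-2 already defines it. A midpoint between Day 1 and Day 336 would be Day 168.5, a much wider window starting at Day 169. Leave the endpoint wording and the off-treatment windows in Tables 3-4 and 3-7 unchanged.

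The cost is a short SAP edit and one window specification, with no new samples. If the SAP is already final, its Section 1 provides for recording the change in the Synoptic CSR. The small downside is that early discontinuers' values leave the by-visit summaries, which the listing or separate row makes good.
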